6.2.3.2 Early Termination at an Individual Study Center

At any time, the study can be terminated at an individual center if:

- The center cannot comply with the requirements of the protocol.
- The center cannot comply with GCP standards.
- The required recruitment rate is not met.

Should the study be prematurely terminated, all study materials must be returned to the Sponsor.

Property of Octapharma. Do not copy or distribute without written permission.

7 ASSESSMENTS AND METHODS

7.1 Demographic and Baseline Information

The following information will be recorded during the Screening Visit:

7.1.1 Demographic and Baseline Characteristics

The demographic and baseline characteristics will include sex, age, race/ethnic origin, and weight.

7.1.2 Medical History

The medical history will be obtained by interviewing the subject and/or review of hospital charts. Records of past diseases and treatments (eg, hospital discharge letters) will be obtained for the study files, if available.

7.1.3 Prior and Concomitant Medication Use

Prior and concomitant medication use will be obtained by interview and/or review of hospital charts. Prior medications are defined as any taken within 1 week of the Screening Visit until the start of IMP infusion. Concomitant medications are defined as any with a start date and time after the start of the Day 1 infusion and their use will be collected throughout the study. Data collected will include the dose, route, and dates and times of administration, the identity of the concomitant medication, the reason for administration, as well as any changes in therapy during the course of the study.

7.1.4 Diagnosis Confirmation

COVID-19 infection will be confirmed using RT-PCR evaluated on nares/throat swab and/or sputum and/or lower respiratory tract samples. A positive result taken in the 7 days prior to Screening is acceptable.

7.2 Efficacy Assessments

7.2.1 Clinical Status

Clinical status categories will be defined according to the following 6-category clinical status scale:

1. Hospital discharge or meet discharge criteria (discharge criteria are defined as clinical recovery, ie, no fever, respiratory rate, oxygen saturation return to normal, and cough relief).
2. Hospitalization, not requiring supplemental oxygen.
3. Hospitalization, requiring supplemental oxygen (but not NIV/HFNC), as defined by A-a Gradient < 150 mmHg.

4. ICU/hospitalization, requiring NIV/HFNC therapy, as defined by A-a Gradient ≥ 150 mmHg.
5. ICU, requiring ECMO and/or IMV.
6. Death.

7.2.2 Oxygenation/Ventilator Status

Oxygenation status and/or ventilation status will be recorded at each scheduled visit, and in between visits if there is a change in status. The following will be captured:

Supportive measure required to maintain oxygen saturation:

- Nasal canula ≤ 4 L/min
- Nasal canula > 4 L/min
- Face mask
- Non-breather face mask
- Non-invasive ventilation
- Invasive mechanical ventilation.

Data will be used to calculate the incidence of invasive mechanical ventilation, duration of invasive mechanical ventilation and other changes in oxygenation status as required.

7.2.3 Viral Clearance

COVID-19 infection status will be re-assessed on Day 7 using an RT-PCR assay to evaluate viral clearance. A nares/throat swab and/or sputum and/or lower respiratory tract sample will be taken for the assessment. If the initial Day 7 RT-PCR test is negative, a repeat test will be performed as soon as possible and no later than at the Day 14 visit.

7.2.4 SpO₂ Saturation and A-a Gradient

SpO₂ will be recorded throughout the study, at a similar time each day, on room-air if possible. Measurements on Days 1 to 4 will be taken *prior to* infusion. Readings on Days 7, 14, 21, and 33 should be taken at approximately the same time each day as the pre-infusion measurements (± 2 hours). The pre-infusion value on Day 1 will serve as the baseline value. If a subject is discharged from the hospital at any time during the course of their participation in the study, a pulse oximeter will be provided to them to monitor their oxygen saturation at home. A call will be made to the subject at approximately the same time as the Day 1 pre-infusion SpO₂ measurement was taken (± 2 hours).

A-a Gradient will be recorded at Baseline (predose on Day 1) and Day 7 only if patient remains at a clinical status of 3 or 4 (see Section 7.2.1) using arterial blood gas (ABG) results. ABGs on Day 7 should be drawn at approximately the same time as the Baseline (Day 1) draw (\pm 2 hours).

7.2.5 Modified Borg Dyspnea Scale

Dyspnea will be measured by the modified Borg Dyspnea Scale which assesses dyspnea on a numerical scale from 0 (representing no dyspnea) to 10 (maximal dyspnea).

Table 3: Modified Borg Dyspnea Scale

Patient Instructions	
The Borg scale is used to help us understand the intensity or severity of your breathing.	
It starts at number 0 where your breathing is causing you no difficulty at all and progresses through to number 10 where your breathing difficulty is maximal.	
How much difficulty is your breathing causing you right now?	
0	Nothing at all
0.5	Very, very slight (just noticeable)
1	Very slight
2	Slight
3	Moderate
4	Somewhat severe
5	Severe
6	
7	Very severe
8	
9	Very, very severe (almost maximal)
10	Maximal

Source: <https://scholarblogs.emory.edu/buddterrace/files/2016/03/Modified-Borg-Dyspnea-Scale.pdf>

7.2.6 McGill Quality of Life

Quality of Life (QoL) will be measured by the McGill Quality of Life Single-Item Scale. The MQoL-SIS (see below) is a validated 1-item multidimensional tool designed to measure physical well-being, physical symptoms, psychological symptoms, existential well-being and support, as well as overall quality of life.

Considering all parts of my life – physical, emotional, social, spiritual, and financial – over the past two (2) days the quality of my life has been:										
0	1	2	3	4	5	6	7	8	9	10
Very bad										Excellent

7.3 Safety Assessments

7.3.1 Assessments for Safety Endpoints

The following drug safety information shall be collected:

- AEs and SAEs temporally associated with the administration of IMP or placebo (for definitions and reporting requirements, see Sections 7.3.2, 7.3.3, and 7.3.3.1)
- Vital signs including SpO₂
- Clinical laboratory evaluations
- Radiological findings as reported on Chest CT or Chest X-ray
- Pregnancies, drug overdose, interaction, medication error, lack of efficacy, and post-study SAEs (see Section 7.3.7).

7.3.2 Adverse Events (AEs)

7.3.2.1 Definitions

Adverse event (AE): An AE is any untoward medical occurrence in a study subject receiving an IMP and which does not necessarily have a causal relationship with this treatment. An AE can therefore be any unfavorable and unintended sign (including an abnormal laboratory finding), symptom, or disease temporally associated with the use of an IMP, whether or not related to the IMP.

Adverse drug reaction (ADR): An ADR is any noxious and unintended response to an IMP related to any dose. The phrase 'response to an IMP' means that a causal relationship between the IMP and an AE carries at least a reasonable possibility, ie, the relationship cannot be ruled out.

Other significant AEs: Any marked laboratory abnormalities or any AEs that lead to an intervention, including withdrawal of drug treatment, dose reduction, or significant additional concomitant therapy.

Withdrawal due to AE/ADR: AE/ADR leading to discontinuation of treatment with IMP. Any such events will be followed up by the Investigator until the event is resolved or until the medical condition of the subject is stable. All follow-up information collected will be made available to the Sponsor.

7.3.2.2 Collection of AEs

The condition of the subject will be monitored throughout the study. At each visit, whether scheduled or unscheduled, AEs will be elicited using a standard nonleading question such as "How have you been since the last visit/during the previous study

period?" In addition, the Investigator will check the subject diaries (if applicable) for any documented event.

Any AE or ADR which occurs during the study will be noted in detail on the appropriate pages of the eCRF. If the subject reports several signs or symptoms representing a single syndrome or diagnosis, the diagnosis should be recorded in the eCRF. The Investigator will grade the severity of all AEs or ADRs (mild, moderate, or severe), the seriousness (non-serious or serious), and the causality as defined in Sections 7.3.2.3, 7.3.3, and 7.3.2.4. The Sponsor is responsible for assessing the expectedness of each ADR (expected or unexpected) as defined in Section 7.3.2.5.

In the event of clinically significant abnormal laboratory findings, the tests will be confirmed, and the subject followed up until the laboratory values have returned to normal and/or an adequate explanation for the abnormality has become available.

Abnormal laboratory results will only be recorded as AEs in the following circumstances:

- The abnormality requires medical intervention or concomitant therapy, and/or
- The abnormality suggests a disease and/or organ toxicity which is assessed as having developed or evolved since Screening.

In all cases, diagnoses should be documented, if possible.

Diseases, signs and symptoms, and/or laboratory abnormalities already present before the first administration of IMP will not be considered AEs unless an exacerbation in intensity or frequency (worsening) occurs.

The Investigator will provide detailed information about any abnormalities and about the nature of and reasons for any action taken as well as any other observations or comments that may be useful for the interpretation and understanding of an AE or ADR.

7.3.2.3 Severity of AEs

The intensity/severity of AEs will be graded as follows:

Mild: an AE, usually transient, which causes discomfort but does not interfere with the subject's routine activities

Moderate: an AE which is sufficiently discomforting to interfere with the subject's routine activities

Severe: an AE which is incapacitating and prevents the pursuit of the subject's routine activities

The grading of an AE is up to the medical judgment of the Investigator and will be decided on a case-by-case basis.

7.3.2.4 Causality of AEs

The relationship of AEs to the administered IMP will be assessed by the Investigator:

Probable: reports including good reasons and sufficient documentation to assume a causal relationship, in the sense of plausible, conceivable, likely, but not necessarily highly probable. A reaction that follows a reasonable temporal sequence from administration of the IMP; or that follows a known or expected response pattern to the suspected medicine; or that is confirmed by stopping or reducing the dosage of the medicine and that could not reasonably be explained by known characteristics of the subject's clinical state.

Possible: reports containing sufficient information to accept the possibility of a causal relationship, in the sense of not impossible and not unlikely, although the connection is uncertain or doubtful, for example because of missing data or insufficient evidence. A reaction that follows a reasonable temporal sequence from administration of the IMP; that follows a known or expected response pattern to the suspected medicine; but that could readily have been produced by a number of other factors.

Unlikely: reports not following a reasonable temporal sequence from IMP administration. An event which may have been produced by the subject's clinical state or by environmental factors or other therapies administered.

Not related (unrelated): events for which sufficient information exists to conclude that the etiology is unrelated to the IMP.

Unclassified: reports which for one reason or another are not yet assessable, eg, because of outstanding information (can only be a temporary assessment).

7.3.2.5 Classification of ADRs by Expectedness

ADRs will be classified by the Sponsor as either expected or unexpected:

Expected: an ADR that is listed in the current edition of the IB or other reference safety information.

Unexpected: an ADR that is not listed in the current edition of the IB or other reference safety information, or that differs because of greater severity or greater specificity.

7.3.2.6 Outcome of AEs

The outcome of all reported AEs will be documented as follows:

1. Recovered, resolved
2. Recovering, resolving
3. Not recovered, not resolved
4. Recovered, resolved with sequelae

5. Fatal
6. Unknown

NOTE: A subject's **death** per se is not an event, but an outcome. The event which resulted in the subject's death must be fully documented and reported, even in case the death occurs within 4 weeks after IMP treatment end and regardless of whether or not it is considered treatment-related.

7.3.2.7 Action(s) Taken

AEs requiring action or therapy must be treated with recognized standards of medical care to protect the health and well-being of the subject. Appropriate resuscitation equipment and medicines must be available on site for anaphylaxis or other emergencies to ensure the best possible treatment. In case of anaphylaxis, the infusion will be stopped, and the subject will be withdrawn from the study.

The action taken by the Investigator must be documented:

a) General actions taken in the event of an AE

- None
- Medication (other than IMP) or other (eg, physical) therapy started
- Test performed
- Other (to be specified)

b) IMP-related actions taken in the event of an AE

- None
- Product withdrawn
- Dose reduced
- Dose increased

The Investigator will follow up on each AE until it has resolved or until the medical condition of the subject has stabilized. Any relevant follow-up information will be reported to the Sponsor.

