1.2 Benefit-Risk Statement

The risks of IVIG administration are well documented. In general, the incidence of adverse events (AEs) associated with IVIG tends to increase with the rate of infusion, and thus the recommended dosage, infusion rates, and monitoring procedures should

be adhered to. Patients that are naïve to IVIG are more at risk than those that are well-maintained and on regular therapy.

Patients with pre-existing risk factors for thrombotic events (such as advanced age, obesity, hypertension, diabetes mellitus and a history of vascular disease or thrombotic episodes, patients with acquired or inherited thrombophilic disorders, patients with prolonged periods of immobilization, severely hypovolemic patients, and patients with diseases which increase blood viscosity) may be at increased risk of developing thromboembolic events (TEEs) (34). Overdose is possible in overweight and elderly patients and in those who have impaired renal function. In patients with signs of cerebral or cardiac ischemia, the increase in viscosity caused by an immunoglobulin infusion may be a risk (34).

The safety profile of *Octagam 10%* based on clinical studies and long-term post-marketing experience is well-documented and detailed in the European Summary of Product Characteristics (SmPC) (35). Adverse drug reactions (ADRs) such as chills, headache, dizziness, fever, vomiting, allergic reactions, nausea, arthralgia, low blood pressure, and moderate low back pain occur occasionally. These adverse effects are mostly transient and mild. However, some very rare adverse effects, including renal impairment, thrombosis, arrhythmia, aseptic meningitis, hemolytic anemia, and transfusion-related acute lung injury, are serious (36). AEs are rarely disabling or fatal, treatment involves supportive measures, and the majority of affected patients have a good prognosis. Reactions to IVIGs tend to be related to the dose and the rate of infusion. Rarely, human normal immunoglobulins may cause a sudden fall in blood pressure and, in isolated cases, anaphylactic shock, even when the patient has shown no hypersensitivity to previous administration. Cases of reversible aseptic meningitis and rare cases of transient cutaneous reactions have been observed with human normal immunoglobulin. Reversible hemolytic reactions have been observed in patients, especially those with blood groups A, B, and AB.

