4.3 Withdrawal and Replacement of Subjects

4.3.1 Premature Subject Withdrawal

Subjects have the right to withdraw from the study at any time for any reason, without the need to justify their decision. The Investigator also has the right to withdraw subjects in case of AEs, poor compliance, or other reasons. Since an excessive rate of withdrawals can render the study non-interpretable, any unnecessary withdrawal of subjects should be avoided.

In addition to the ongoing safety monitoring and periodic Independent Data Monitoring Committee (IDMC) data review, the following rule will be implemented to apply temporary suspension of study drug administration, pending a safety investigation, for an unacceptable increased venous TEE or acute renal failure risk in the *Octagam 10%* group compared to the placebo group:

- For both venous TEEs or acute renal failures, the event risk will be calculated separately as (number of events reported)/(number of daily infusions) in both treatment groups, and the 90% confidence interval (CI) for the resulting risk ratio (R_{Octagam}/R_{Placebo}) will be determined by means of the / relrisk option of the SAS procedure FREQ. In case no events are observed in the placebo group, 1 will be added to each cell in the 2X2 table to enable this risk ratio evaluation. The stopping rule will be triggered if the lower confidence limit is greater than 1.0.
- This stopping rule will be applied whenever an unblinded evaluation is done, and a total of 40 daily infusions or more have been administered.
- For the first 40 daily infusions (ie, first 10 subjects that complete infusion cycle per protocol) a fixed rule will be applied by the IDMC to temporarily suspend study drug administration in case the number of related serious TEEs or acute renal failures as assessed by IDMC in the *Octagam 10%* group is triple the number in the placebo group. If no TEE or acute renal failure is observed in the

placebo group during this initial study phase, temporary suspension of study drug administration and safety investigation will be initiated if three related serious TEEs as assessed by IDMC or acute renal failures have been reported in the *Octagam 10%* group.

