For any withdrawals after study entry, the Investigator will obtain all the required details and document the reason(s) for discontinuation. If the reason for withdrawal of a subject is an AE, the main specific event or laboratory test will be recorded, and the Investigator will make thorough efforts to clearly document the outcome.

Other reasons for premature termination of subjects may be:

- Withdrawal of subject's consent.
- Pregnant and lactating subjects will be immediately excluded from the study.
- Investigator's opinion that the subject may be severely harmed if he/she continues study participation, namely by the treatment and procedures requested by the study protocol.
- Occurrence of a condition or disease that interferes with the study treatment or represents an exclusion criterion.
- Administration of IVIG other than *Octagam 10%*.
- Subjects do not comply with the study protocol.

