5.4 Dose and Dosing Schedule

Octagam 10% is available in glass bottles with different volumes of human immunoglobulin. Glass bottles of different volume should be combined in order to reach the required amount of IgG.

Octagam 10% or placebo will be administered by intravenous infusions on 4 consecutive days. The amount of *Octagam 10%* calculated on the dosage delivery schedule is 2 g/kg divided evenly over 4 days (0.5 g/kg/day).

If a subject is randomized to receive placebo, the same volume with the same infusion rate as would have been applied in case the subject would have been randomized to

2.0 g/kg *Octagam 10%* will be used. Therefore, they will receive an equal dose of placebo given over 4 days.

Body weight is to be measured at Screening or within 24 hours of first IMP administration and reported to the pharmacist or designee as it is needed for the preparation of the following study medication dosages.

All subjects should be clinically assessed for being adequately hydrated prior to IMP administration. TEE prophylaxis should be considered.

The initial infusion rate for each infusion episode will be:

- 0.01 mL/kg/min (60 mg/kg/h) for the first 30 minutes (\pm 5 minutes)
- if tolerated, advanced to 0.02 mL/kg/min (120 mg/kg/h) for the next 30 minutes (\pm 5 minutes)
- if tolerated, advanced to 0.04 mL/kg/min (240 mg/kg/h) for the remainder of the infusion

The interval of 30 minutes may be prolonged as per discretion of the investigator.

In subjects at risk for thromboembolic adverse reactions and acute renal failure (such as advanced age, hypertension, history of thrombotic episodes, subjects with prolonged periods of immobilization, concomitant nephrotoxic medication, diabetes mellitus, overweight, hypovolemia), *Octagam 10%* should be administered at the minimum rate of infusion practicable.

If AEs occur during the infusion, the rate is to be reduced to half the rate at which the event occurred, or the infusion is to be interrupted until symptoms subside. The infusion may then be resumed at a rate tolerated by the subject. In case of severe hypersensitivity or anaphylaxis, the infusion will not be restarted and all treatment with the IMP will be withdrawn. The subject will continue to be followed up in accordance with study-specific procedures as specified in the protocol with the exception that no further administrations of IMP will be performed. The subject will receive ongoing treatment in accordance with local SOC.

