6.1.7 Subject Early Discontinuation

A study subject has a right to refuse study treatment and study visits at any time and for any reason. A subject can also withdraw from the study or study drug treatment for AEs, in which case the subject will be followed until resolution of the AE. Every effort will be made to assess the effect and outcome of the AE.

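### After anaphylaxis, Protocol 7.3.2.7 takes the subject out of the study, while Protocol 5.4 stops only the IMP and keeps follow-up going; both are mandatory and neither says which prevails

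*Protocol*

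**What the plan says.** Protocol 7.3.2.7 (Action(s) Taken) says: "In case of anaphylaxis, the infusion will be stopped, and the subject will be withdrawn from the study".

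Protocol 5.4 (Dose and Dosing Schedule) deals with the same event: "In case of severe hypersensitivity or anaphylaxis, the infusion will not be restarted and all treatment with the IMP will be withdrawn". It goes on: "The subject will continue to be followed up in accordance with study-specific procedures as specified in the protocol". The only exception it makes is that no more IMP is given.

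Two other sections bear on how to read these instructions. Protocol 7.3.2.1 defines withdrawal due to an AE or ADR as "AE/ADR leading to discontinuation of treatment with IMP". Protocol 6.1.7 treats leaving the study and stopping the drug as two different things: "A subject can also withdraw from the study or study drug treatment for AEs".

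The primary and secondary efficacy analyses are by ITT (Protocol 9.2.3.2; SAP 13 and 14), and five of the six key secondary endpoints run through Day 33.

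**The concern.** An investigator with a subject in anaphylaxis finds two instructions. One ends participation in the study. The other ends dosing and leaves the visit schedule in place. Nothing says which governs, so sites may act differently.

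What is at stake is outcome data on a randomised subject. If participation ends, the remaining clinical status visits and the ICU, ventilation and discharge dates may never be recorded, and the analysis uses values set by rule. The loss would also follow a reaction to the infusion. Protocol 1.2 links anaphylactic shock to immunoglobulin, so it could fall more on one arm than the other.

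**Working it through.** The point rests on the text, so the passages come first and the arithmetic only gives the size.

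**Can the two sections be reconciled?**

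| Question | Protocol 5.4 | Protocol 7.3.2.7 |
|---|---|---|
| Event | Severe hypersensitivity or anaphylaxis | Anaphylaxis |
| Infusion | Not restarted | Stopped |
| What the subject leaves | IMP treatment | The study |
| Scheduled follow-up | Continues | Ends with participation |
| Force | Mandatory | Mandatory |
| Cross-reference | None | None |

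The overlap is anaphylaxis only. Severe hypersensitivity without anaphylaxis appears in 5.4 alone, so no conflict arises there.

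The 7.3.2.1 definition suggests that stopping the IMP may be what was meant. It does not settle the matter, for three reasons:
- 7.3.2.7 does not use the defined term; it names the study.
- 7.3.2.7 lists withdrawal of the product as a separate IMP-related action.
- 6.1.7 keeps study withdrawal and drug withdrawal apart.

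**What replaces the lost data?**

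| Endpoint | Rule for a withdrawn subject | Source |
|---|---|---|
| Day 7 and Day 14 status | LOCF, overridden by a known worse state (death, ECMO/IMV, ICU); failure if there is no post-baseline status | Protocol 9.2.5; SAP 4.1 |
| Hospital stay | Censored at Day 33 if the end date is missing | Protocol 9.2.3.2; SAP 14 |
| Severe progression | No event, unless there is evidence of one | Protocol 9.2.5; SAP 4.1 |
| ICU or IMV days, ongoing with no usable end date | Run to a projected Day 33 | Protocol 9.2.3.2; SAP 14 |

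The severe-progression rule favours the arm of the withdrawn subject. The hospital-stay rule and the projected Day 33 rule work against it. The status rule can go either way. No net direction follows.

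**Size per subject.** Status is scheduled on Days 2, 3, 4, 7, 14, 21 and 33 after baseline, and before the infusion on dosing days (Protocol Table 1 and 6.1.2).
- Withdrawn at infusion 1: all 7 assessments are lost, and Day 7 is scored a failure.
- Withdrawn at infusion 2, 3 or 4: 6, 5 or 4 are lost, and LOCF applies.
- Largest effect of one subject on the IVIG Day 7 rate, with 104 per arm: 1/104 = 0.96 percentage points. Against the planned difference of 80% - 60% = 20 points, that is 0.96/20 = 4.8%.
- A subject in the ICU at randomisation on Day 1, with no usable end date, is given 33 - 1 + 1 = 33 ICU days.

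**Does other follow-up fill the gap?**
- AEs are followed until they resolve or the subject is stable (Protocol 6.1.7, 7.3.2.7). That is not the visit schedule.
- SAEs and deaths are reportable for 4 weeks after the last IMP (Protocol 7.3.7). Last IMP day + 28 gives Day 29 for infusion 1 and Day 32 for infusion 4, which is 4 to 1 days short of Day 33. SAEs depend on the investigator learning of them, and active monitoring is not required.
- Registry contact continues after early termination, but only every three months (Protocol Table 2).

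None of these schedules clinical status or collects ICU and discharge dates.

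**Power.** At 60% against 80%, two-sided 0.05 and 88 per arm, power is 0.831, which agrees with the stated minimum of 80%. 176/0.85 = 207.1, or 208 in whole pairs. The drop-out allowance is 208 - 176 = 32 subjects, so a few withdrawals of this kind do not change the sample size case.

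**The case against.** The best reply is that 7.3.2.7 is a drafting slip. Section 5.4 is the operative dosing section and spells out the follow-up. Section 7.3.2.7 is about recording actions taken, and the 7.3.2.1 definition points to stopping the IMP. On that reading most sites would do the right thing. This is plausible, and it is a reason to rate the point minor. It does not remove the conflict, because a coordinator who opens 7.3.2.7 alone is told to end study participation.

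It is also fair that safety follow-up continues, that such cases should be rare ("in isolated cases, anaphylactic shock"), and that a prior serious allergic reaction to IVIG is an exclusion (Protocol 4.1.2). All of that stands and limits the size.

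Timing is a further objection. Version 08 is dated 27 January 2021, after the planned core end in Q4 2020, and the SAP introduction reports accelerated enrolment. The documents do not give enrolment status, but a change in wording may reach few new subjects. That stands too, and it shifts the practical value towards the data-review step.

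A reader might infer that Protocol 4.3.1 has the same fault, since its possible reasons for ending participation include "Occurrence of a condition or disease that interferes with the study treatment or represents an exclusion criterion". The documents do not support that. The list is permissive, and the same section says that "any unnecessary withdrawal of subjects should be avoided". There is no contradiction to correct there.

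**Conclusion.** The inconsistency is certain for anaphylaxis, and the text of 7.3.2.7 is wrong as it stands. The data loss is possible but not shown. The point is minor: probably very few subjects, at most 0.96 points on the IVIG Day 7 rate for each, uncertain direction, no effect on power. This assumes 104 subjects in the arm and that a site reads 7.3.2.7 literally. The documents give no rate of anaphylaxis or of withdrawal for it, so no total effect can be stated.

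Three stronger or firmer conclusions are tempting and should not be drawn:
- *That the results would be biased towards one arm.* The rules pull in different directions, and nothing supports a success rate for a partly dosed subject with anaphylaxis from which to compute an expected shift.
- *That the planned sensitivity analyses bound the loss.* For withdrawals they address clinical status and severe progression only (Protocol 9.2.5; SAP 4.1 and 13). None addresses hospital, ICU or IMV durations missing through withdrawal. The all-failure and complete-case analyses do not bound a difference between arms either.
- *That a withdrawn subject with no later record is given zero ICU or IMV days.* The zero is defined for subjects not admitted to the ICU or not needing IMV; applying it to unobserved time is an inference.

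**What to change.** Replace the sentence in Protocol 7.3.2.7 with: *the infusion will be stopped and IMP permanently withdrawn; the subject continues to be followed per protocol to Day 33 (see Section 5.4)*. Protocol 4.2 already takes this approach after prohibited medication: infusions stop and follow-up continues.

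At the blinded data review (SAP 7), list any subject already withdrawn under 7.3.2.7 and complete the outcomes to Day 33 from hospital records where consent still allows.

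The cost is a one-sentence amendment, submitted to the ethics committee and/or authority as regulations require (Protocol 10.4), and a letter to about 20 sites in three countries. No SAP text, sample size or procedure changes. If enrolment is complete or nearly so, the data-review step is the part that still matters.
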